## 6.0 Study Design

This is a single-center, multiple-dose, randomized, double-blind, placebo-controlled, positive-controlled, twelve sequence 3-period cross-over study.

At the start of treatment period 1, at the end of Day -1, subjects will be randomized to one of the 12 treatment sequences comprised of 3 of the 4 treatments described in [6.2](#). All subjects will receive treatments A and B, half will receive treatment C, and the other half will receive treatment D. Each treatment period consists of 15 dosing days. Following each treatment period, subjects will undergo a washout period lasting a minimum of 13 and a maximum of 20 days from the last dose of study drug.

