Ctrough	Predose concentration prior to each daily dose from Day 11 to Day 14	Balovaptan, M2, M3	A: 11 to 14 B: 11 to 14	Taken directly from the observed plasma concentration-time data

Descriptive statistics (n, mean, geometric mean, SD, %CV, median, min, and max) will be used to summarize the calculated PK parameters by treatment. For Tmax, only median, min and max will be presented.

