#### 16.2.2.1 Steady State

A linear plot of the arithmetic mean trough (predose) plasma concentrations versus time will be provided for Balovaptan on days 11 through 14 to visually assess the achievement of steady state. This plot will show time in days.

In addition, a statistical evaluation of steady state will also be made by dose level using the trough plasma concentrations. All valid trough concentrations on the natural-log scale will be analyzed using an analysis of variance (ANOVA) model with study day as a fixed effect. From this model, orthogonal contrasts with 95% confidence intervals (CIs) will be formed between the adjusted mean trough concentration at each study day and the mean trough concentrations for all the following study days using Helmert contrasts. Precisely, Day 11 will be compared to Day 12 through Day 14 combined; Day 12 will be compared to Day 13 through Day 14 combined; and so on.

The following SAS PROC MIXED pseudo-code may be used:

```
proc mixed data= adpc;
  by treatment;
  class day;
  model ln(trough concentration) = day / solution;
  lsmeans day / cl alpha=.05;
  estimate "Day 11 vs Days 12 - 14" day 3 -1 -1 -1 / e cl alpha=0.05
  divisor=3;
  estimate "Day 12 vs Days 13 - 14" day 0 2 -1 -1 / e cl alpha=0.05
  divisor=2;
  estimate "Day 13 vs 14" day 0 0 1 -1 / e cl alpha=0.05 divisor=2;
run;
```

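### The steady-state trough model has no subject term, so its confidence intervals are mis-sized, and the sample code halves the Day 13 versus Day 14 difference

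*SAP*

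**What the plan says.** SAP 16.2.2.1 (Steady State) plans a statistical evaluation by dose level, using all valid troughs on the natural-log scale. The model is an "analysis of variance (ANOVA) model with study day as a fixed effect". The sample PROC MIXED code agrees: it runs by treatment, has day as its only class variable, and states "model ln(trough concentration) = day / solution". It contains no random or repeated statement.

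The contrasts are Helmert contrasts with 95% confidence intervals, each comparing one day's mean with the mean of all the days that follow: Day 11 against Days 12 to 14, then "Day 12 will be compared to Day 13 through Day 14 combined; and so on". The code gives the first two contrasts divisors of 3 and 2. The last, for Day 13 against Day 14, is "day 0 0 1 -1 / e cl alpha=0.05 divisor=2".

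On the data structure, SAP 6.0 says "All subjects will receive treatments A and B", and SAP 16.2.2 defines the trough as "Predose concentration prior to each daily dose from Day 11 to Day 14". The result is reported in Table 14.2.2.3 (SAP Appendix 4) and serves the time-to-steady-state parameter in Protocol 6.6.

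**The concern.** There are two separate faults.

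**Error term.** Within each treatment, the same subjects are measured on all four days. A subject with generally high troughs is high on every day, so that level drops out of any comparison between days. A model with day alone leaves it in the residual and treats the four values as independent. The point estimates for the Day 11 and Day 12 contrasts are unaffected with complete data, but their standard errors and intervals are wrong. SAP 9.4.3 plans no formal hypothesis testing, so the estimates and intervals are themselves the product of this analysis.

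**Divisor.** The code for Day 13 versus Day 14 does not compute what the SAP text defines. If programmed as shown, the estimate, standard error and both limits are half their proper size. They would disagree with the day means that the same code requests ("lsmeans day / cl alpha=.05") and with the descriptive statistics that "will be used to summarize the calculated PK parameters by treatment".

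**Working it through.** **1. Coefficients against the stated definition**

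Dividing each printed coefficient set (Days 11, 12, 13, 14) by its printed divisor:

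| Contrast | Coefficients | Divisor | Result | Matches the text? |
|---|---|---|---|---|
| Day 11 vs 12–14 | 3, -1, -1, -1 | 3 | 1, -1/3, -1/3, -1/3 | yes |
| Day 12 vs 13–14 | 0, 2, -1, -1 | 2 | 0, 1, -1/2, -1/2 | yes |
| Day 13 vs 14 | 0, 0, 1, -1 | 2 | 0, 0, 1/2, -1/2 | no, half the difference |

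On back-transformation the third gives exp(0.5 × ln R) = √R, where R is the true Day 13/Day 14 ratio: R = 0.80 gives 0.894 and R = 0.90 gives 0.949. Because estimate and standard error are halved together, t, p and whether the interval includes zero do not change.

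**2. Width of the intervals without a subject term**

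Take n subjects with complete data, total log-scale variance s² and equal correlation ρ between days within a subject. For a contrast c:

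- variance used by the planned model: s² Σc² / n
- true variance: s² (1 − ρ) Σc² / n
- width ratio, planned to correct: 1/√(1 − ρ)

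The documents give no ρ, so a range is shown:

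| ρ (assumed) | Width ratio, any contrast |
|---|---|
| 0.5 | 1.41 |
| 0.75 | 2.00 |
| 0.8 | 2.24 |
| 0.9 | 3.16 |

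The degrees of freedom barely matter. At n = 48 the critical value is 1.9727 with 4n − 4 = 188 df as written, and 1.9769 with 3(n − 1) = 141 df when subject is included, a difference of 0.2%.

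In 4,000 simulated data sets per ρ at n = 48, mean width ratios were 1.42, 2.00, 2.23 and 3.16. The nominal 95% interval for the Day 11 contrast covered 99.3% at ρ = 0.5 and at least 99.95% from 0.75 upward. With subject in the model, coverage was 94.9 to 95.4%.

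If correlation instead decays with lag (AR(1), matrix R, adjacent-day ρ), the ratio is √(c′c / c′Rc):

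| ρ (assumed) | Day 11 contrast | Day 12 contrast | Day 13 contrast |
|---|---|---|---|
| 0.5 | 1.14 | 1.22 | 1.41 |
| 0.8 | 1.59 | 1.81 | 2.24 |
| 0.9 | 2.15 | 2.50 | 3.16 |

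The inflation is smaller for the first two contrasts, but the direction is the same.

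**3. Both faults together, Day 13 versus Day 14**

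Under equal correlation the coded interval is 0.5/√(1 − ρ) times the correct width: 0.71 at ρ = 0.5, 1.00 at 0.75, 1.12 at 0.8 and 1.58 at 0.9. It can be too narrow or too wide, and it is centred on half the true difference in every case.

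**4. What the data are likely to show**

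Protocol 1.2.1.1 gives a half-life of about 46 h. With simple accumulation, the fraction remaining after 24 h is r = exp(−ln 2 × 24/46) = 0.6965, and the trough before the Day d dose is 1 − r^(d−1) of plateau:

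- Day 11: 0.9731; Day 12: 0.9813; Day 13: 0.9870; Day 14: 0.9909
- Day 11 against the geometric mean of Days 12–14: 0.987
- Day 12 against the geometric mean of Days 13–14: 0.992
- Day 13 against Day 14: 0.996, which the divisor turns into √0.996 = 0.998

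For the parent drug, then, the expected differences are small.

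**5. Effect on detecting a real drift (assumed values)**

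With n = 48 and assumed trough CVs of 40% between and 15% within subjects, the half-width for the Day 11 contrast on the log scale falls from 0.136 to 0.049 once subject is included. In 10,000 simulated trials with the Day 11 trough truly 10% below Days 12–14, the interval excluded zero in 14% as written and 99% with subject included. For a 5% shortfall the figures were 0.2% and 54%. No document suggests shortfalls of that size; this shows only how much resolution the planned model gives up.

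**The case against.** The best defence is about weight. This is one secondary, descriptive table, shown alongside a trough plot. Protocol 3.3.1.1 already reports steady state after about 7 days for balovaptan and 10 days for M3. At the projected Day 11 ratio of 0.987 (log difference 0.0135), with the assumed 15% within-subject CV, the correct standard error is about 0.025, so even the corrected model would exclude zero in only about 8% of trials. The SAP gives no decision rule either. Wide intervals favour a steady-state reading only if the criterion is that the interval includes zero; under an equivalence reading they would be conservative. The code is pseudo-code that may be used, its text definition is right, and a programmer could catch the divisor. The SAP does not say that results will be back-transformed, and the table shells are in a separate document.

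Most of this stands as a limit on the consequences. The sizes of inflation rest on assumed correlations, the ratios of 0.894 and 0.949 apply only if results are back-transformed, and no bias in a particular conclusion is established. It does not remove the faults. The optional status of the code excuses only the divisor, because the missing subject term is in the governing text as well. SAP 9.4.2, which names no predetermined covariates, does not supply one. The half-life argument covers the parent only: Protocol 3.3.1.1 says the M2 time course has not been closely studied and reports its steady state at 10 mg only, while Protocol 6.6 lists time to steady state for M2 (as appropriate) and M3 too.

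**Conclusion.** Both faults hold.

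- **Subject term.** The planned model uses the wrong error term for repeated troughs. Given positive within-subject correlation, its intervals are too wide, by 1.41 to 3.16 times for equal correlations of 0.5 to 0.9. The direction follows from the design; the size depends on a correlation the documents do not give.
- **Divisor.** If the code is used as printed, the Day 13 versus Day 14 log difference and its limits are exactly half what the SAP text defines. Inference about zero is unchanged by the divisor.

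The reach is Table 14.2.2.3 only. The primary QTcF analysis is untouched, the expected numerical harm for the parent drug is small, and a changed steady-state conclusion is not shown. It should be fixed because the plan is wrong as written and the correction is nearly free.

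**What to change.** In the text of SAP 16.2.2.1, specify study day as a fixed effect and subject as a random effect. In the code, add subject to the class statement and add `random subject;` (or `repeated day / subject=subject type=un;`). Delete `divisor=2` from the Day 13 versus Day 14 estimate only; the divisors of the other two contrasts are right.

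The cost is one phrase of text and a few tokens of code before database lock. No new data or change to study conduct is needed.

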6.6 PHARMACOKINETIC ANALYSES

Subjects will be excluded from the PK analysis population if they significantly violate the inclusion or exclusion criteria, deviate significantly from the protocol, or if data are unavailable or incomplete. Excluded cases will be documented together with the reason for exclusion. All decisions on exclusions from the analysis will be made prior to database closure.

Pharmacokinetics are a secondary objective of this study. The specific objectives are

- To investigate the pharmacokinetics of balovaptan, M2 (as appropriate), and M3.
- To investigate the pharmacokinetics of moxifloxacin.

Individual plasma concentrations at each sampling timepoint for balovaptan, M2 (as appropriate), M3, and moxifloxacin will be presented by listings and descriptive summary statistics by treatment, including means, geometric means, ranges, standard deviations and coefficients of variation. Individual and mean concentration versus time will be plotted on linear and semi-logarithmic scales.

PK parameters will be estimated using standard non-compartmental methods. All PK parameters for balovaptan, M2 (as appropriate), and M3 will be presented by individual listings and summary statistics by treatment including means, geometric means, medians, ranges, standard deviations and coefficients of variation.

The following balovaptan, M2 (as appropriate), M3 PK parameters will be estimated:

- Cmax: Day 1 and Day 14 for Treatment A and B
- AUC0-24h: Day 1 and Day 14 for Treatment A and B
- Tmax: Day 1 and Day 14 for Treatment A and B
- Ctrough: Day 11, 12, 13, 14 for Treatment A and B
- Time to steady state for Treatment A and B

The following moxifloxacin PK parameters will be estimated:

- Cmax, AUC0-24h, and Tmax will be estimated on Days 2 (Treatment C) or 15 (Treatment D)

Additional PK analyses maybe be conducted as appropriate for balovaptan, M2 (as appropriate), M3 and moxifloxacin.

Subjects will be excluded from the PK analysis population if they significantly violate the inclusion or exclusion criteria, deviate significantly from the protocol, or if data are unavailable or incomplete. Excluded cases will be documented together with the reason for exclusion. All decisions on exclusions from the analysis will be made prior to database closure.

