6.7.3 By-Time Point Analysis

The statistical hypothesis to be tested for the primary assessment of QT prolongation for each dose of the balovaptan treatment is:

$$H_0: \cup \{\mu_{D(i)} - \mu_{P(i)}\} \geq 10, i = 1, 2, \dots, 7$$

$$H_1: \cap \{\mu_{D(i)} - \mu_{P(i)}\} < 10, i = 1, 2, \dots, 7$$

where $\mu_{D(i)}$ and $\mu_{P(i)}$ are the least squares (LS) mean of Δ QTcF for each dose of balovaptan and placebo at time point i on Day 14, respectively.

The “by-time point” analysis for QTcF will be based on a linear mixed-effects model with change-from-baseline QTcF (Δ QTcF) as the dependent variable; gender, period, sequence, time (categorical), treatment (balovaptan, and placebo), and time-by-treatment interaction as fixed effects; and baseline QTcF as a covariate. An unstructured covariance matrix will be specified for the repeated measures at time points for subject within treatment period. If the model with an unstructured covariance matrix fails to converge, other covariance matrices such as compound symmetry and autoregressive will be considered. If the fixed effects for period and/or sequence should prove to be nonsignificant (i.e., if the p value > 0.1), these effects may be removed from the model.

and the analysis will be repeated without those covariates. From this analysis, the LS mean and 2-sided 90 % CI will be calculated for the contrast “balovaptan versus placebo” at each dose of balovaptan and each post-dose time point on Day 1 and Day 14, separately. If the upper bound of the CI lies below 10 ms for the highest dose group of balovaptan at all seven post-dose time points (0.5, 1.25, 2.5, 4, 8, 12, and 24 hours) on Day 14 (steady state), balovaptan will be concluded not to have a significant effect on QT interval prolongation.

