### 9.4.3 Hypothesis Testing

No formal hypothesis testing will be done.

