## Appendix 4: List of End of Text Outputs

### List of End of Text Tables and Figures:

Output	Title	Analysis Set
Section 14.1 – Disposition and Demographic Data		
Table 14.1.1	Summary of Subject Disposition	All
Table 14.1.2	Summary of Demographics	All
Table 14.1.3	Summary of Study Drug Administration	Safety
Section 14.2.2 – PK Data		
Table 14.2.2.1.1	Summary of Balovaptan Plasma Concentrations	PK
Table 14.2.2.1.2	Summary of Moxifloxacin Plasma Concentrations	PK
Table 14.2.2.2.1	Summary of Balovaptan Plasma Pharmacokinetic Parameters	PK
Table 14.2.2.2.2	Summary of Moxifloxacin Plasma Pharmacokinetic Parameters	PK
Table 14.2.2.3	Statistical Analysis to Determine Time to Steady State	PK
Figure 14.2.2.4.1	Plot of Mean ( $\pm$ SD) Balovaptan Plasma Concentrations on Day 1 versus Time on a Linear Scale	PK
Figure 14.2.2.4.2	Plot of Mean Balovaptan Plasma Concentrations on Day 1 versus Time on a Semi-Log Scale	PK
Figure 14.2.2.4.3	Plot of Mean ( $\pm$ SD) Balovaptan Plasma Trough Concentrations versus Time on a Linear Scale	PK
Figure 14.2.2.5.1	Plot of Mean ( $\pm$ SD) Moxifloxacin Plasma Concentrations versus Time on a Linear Scale	PK
Figure 14.2.2.5.2	Plot of Mean Moxifloxacin Plasma Concentrations versus Time on a Semi-Log Scale	PK
Figure 14.2.2.6.1	Plot of Individual Balovaptan Plasma Concentrations on Day 1 versus Time on a Linear Scale	PK
Figure 14.2.2.6.2	Plot of Individual Balovaptan Plasma Concentrations on Day 1 versus Time on a Semi-Log Scale	PK
Figure 14.2.2.7.1	Plot of Individual Moxifloxacin Plasma Concentrations versus Time on a Linear Scale	PK
Figure 14.2.2.7.2	Plot of Individual Moxifloxacin Plasma Concentrations versus Time on a Semi-Log Scale	PK
Figure 14.2.2.8.1	Scatter Plot of Individual Balovaptan Plasma Pharmacokinetic Parameters	PK
Figure 14.2.2.8.2	Scatter Plot of Individual Moxifloxacin Plasma Pharmacokinetic Parameters	PK
Section 14.3 – Safety Data		
Table 14.3.1.1	Summary of Adverse Events	Safety

Table 14.3.1.2	Summary of Treatment Emergent Adverse Events by System Organ Class and Preferred Term	Safety
Table 14.3.1.3	Summary of Treatment Emergent Adverse Events by Relationship to Study Drugs	Safety
Table 14.3.1.4	Summary of Treatment Emergent Adverse Events by Severity	Safety
Table 14.3.2	Listing of Serious Adverse Events	All Subjects
Table 14.3.3	Not part of TFL – Reserved for Narratives in CSR	
Table 14.3.4	Listing of Abnormal Laboratory Values	All Subjects
Table 14.3.5	Summary of Laboratory Results	Safety

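### The SAP's statistical evaluation of steady state gives difference contrasts with no tolerance or decision rule, from a day-only model, and its code halves the Day 13 vs 14 contrast

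*SAP*

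**What the plan says.** Protocol 6.6 lists "Time to steady state for Treatment A and B" among the PK parameters to be estimated. SAP 16.2.2.1 serves this in two ways. One is a plot of arithmetic mean balovaptan troughs "on days 11 through 14 to visually assess the achievement of steady state". The other is numerical: "a statistical evaluation of steady state will also be made by dose level using the trough plasma concentrations".

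For the numerical part, log troughs are "analyzed using an analysis of variance (ANOVA) model with study day as a fixed effect". No other term is named, and the SAS pseudo-code has only day in the model, with no subject term. The SAP then states: "From this model, orthogonal contrasts with 95% confidence intervals (CIs) will be formed between the adjusted mean trough concentration at each study day". These are Helmert contrasts, which set each day against the average of those after it. In the code, the Day 13 vs 14 contrast has coefficients 1 and -1 with `divisor=2`.

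SAP Appendix 4 titles the resulting Table 14.2.2.3 "Statistical Analysis to Determine Time to Steady State". SAP 9.4.3 states: "No formal hypothesis testing will be done". No tolerance, reference value or acceptance rule for steady state appears in either document.

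**The concern.** Steady state is a claim of similarity: the trough on one day equals the later troughs to within some tolerance. A CI for a difference can support that claim only when it is compared with a stated tolerance. Here a table whose title promises a determination has no rule by which to determine anything.

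With no other reference value, the natural default is to ask whether the CI covers zero. That answer depends on the width of the CI as well as on how close the troughs are. Width is a particular problem here, because a day-only model leaves between-subject variation in the error term although each subject contributes all four troughs. A wide CI would then be read as reassurance.

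The label matters somewhat, because Protocol 6.7.3 describes the primary analysis day as steady state: if all upper bounds are below 10 ms "on Day 14 (steady state), balovaptan will be concluded not to have a significant effect on QT interval prolongation".

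**Working it through.** The steady-state section states no power, margin or criterion, so there is no figure of the plan's own to reproduce. The check asks what the contrasts can and cannot distinguish.

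**Inputs.** From the documents: 48 evaluable subjects, all receiving both balovaptan doses; troughs on Days 11, 12, 13 and 14; balovaptan half-life about 46 h (Protocol 1.2.1.1); plateau after about 7 days for balovaptan and 10 days for M3 (Protocol 3.3.1.1). The documents give no trough variability. Assumed: within-subject log SD 0.15 (range 0.10 to 0.20) and total log SD 0.3 to 0.7.

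**1. Day 11 vs Days 12-14, model as written, CI read against zero.**
- SE factor: sqrt(1/48 + 1/144) = 1/6.
- The 95% half-width the model reports (188 df, t = 1.973) is 1.973 × total SD / 6 = 0.099, 0.164 and 0.230 at total SD 0.3, 0.5 and 0.7.
- The true SE of the contrast is smaller, because subject effects cancel: 0.15 / 6 = 0.025.
- P(CI covers 0) ≈ Φ((half-width − |ln ratio|) / 0.025), with |ln 0.90| = 0.105 and |ln 0.85| = 0.163.

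| Day 11 relative to later mean | Total SD 0.3 | 0.5 | 0.7 |
|---|---|---|---|
| 10% below | 39% | 99% | 100% |
| 15% below | 0.5% | 53% | 99.7% |

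At within-subject SD 0.10 or 0.20 the true SE is 0.0167 or 0.0333. The 10% row then runs from 34% to 42% at total SD 0.3 and is at least 96% at 0.5 and 0.7.

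A simulation of all three contrasts as coded (between-subject SD 0.4, within-subject SD 0.15) agrees in direction. A 5% rise per day, about 16% over Days 11 to 14 (1.05³ = 1.158), leaves every CI covering zero in 92.5% of runs.

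**2. The same contrast with a subject effect (141 df, t = 1.977).**
- 10% deficit at SD 0.15: Φ(1.977 − 0.105/0.025) ≈ 1.3% still cover zero. At SD 0.20 it is about 12%.
- The opposite error now appears. A 5% difference excludes zero in about 86%, 53% and 33% of trials at within-subject SD 0.10, 0.15 and 0.20. Perfectly flat troughs have at least one of the three unadjusted CIs excluding zero in about 14% of runs.

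So most of the wrong acceptances come from the missing subject term. Adding it while still reading against zero makes small differences the problem, so the criterion is needed as well.

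**3. Day 13 vs 14.** Coefficients 1 and -1 with a divisor of 2 give (Day 13 − Day 14)/2 and half its CI. Whether the CI covers zero is unaffected, but any tolerance is effectively doubled on the log scale. A 25% one-day rise, ln 1.25 = 0.223, would be reported as 0.112, a ratio of about 1.12.

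**4. What is expected for balovaptan.** With simple accumulation, the fraction of plateau is 1 − exp(−ln 2 × t/46). The Day 11 predose sample (240 h) is at 97.3% and Day 14 (312 h) at 99.1%. The expected ratio of Day 11 to Days 12-14 is about 0.987, a shortfall of about 1.4%.

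**5. A tolerance rule, illustrated with 0.80 to 1.25.** With the subject effect and SD 0.15, the 90% CI for Day 11 vs 12-14 lies inside in about 100% of trials at a true ratio of 0.95, 99.9% at 0.90 and 5% at 0.80. Without the subject effect, at total SD 0.7, the 90% half-width for the full Day 13 vs 14 difference is 1.653 × 0.7 × sqrt(2/48) = 0.236. That exceeds ln 1.25 = 0.223, so even flat troughs could not be expected to pass.

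**The case against.** The SAP never says that the CIs are compared with zero, SAP 9.4.3 disclaims formal testing, and a plot accompanies the contrasts. The code is offered as pseudo-code that may be used, and the table shells are in a separate document, so ratios may appear there. All of this stands. The defect is the absence of a stated criterion, not the presence of a wrong one.

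Three stronger readings are tempting, and the documents do not support them.
- A reader might infer that the plan would flag trivial differences. Under the day-only model it almost never would: at within-subject SD 0.15 a 5% difference excludes zero in about 3% of trials at total SD 0.3, and in essentially none at 0.5 or 0.7.
- A reader might infer that these contrasts cannot show steady state at all. They can: a log difference with its CI becomes a ratio that can be set against a tolerance fixed in advance.
- A reader might infer that the primary analysis is at risk. The 10 ms rule in Protocol 6.7.3 is not conditional on Table 14.2.2.3, and Day 14 carries the steady-state label on the strength of earlier PK data.

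It is also fair that a 10% deficit is far from the 1.4% expected for balovaptan. That estimate is approximate, since Protocol 3.3.1.1 calls the multiple-dose PK time-dependent, and it covers the parent drug only.

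**Conclusion.** The point holds as a gap in specification. A table titled as a determination of time to steady state has no tolerance and no decision rule. Under the default reading, the day-only model could accept a 10% Day 11 deficit in about 39% to 100% of trials, depending on total log SD from 0.3 to 0.7. Those figures rest on assumed variability with 48 subjects, and most of the effect comes from the missing subject term. The halved Day 13 vs 14 contrast is a plain error in the code as printed.

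The analysis also cannot estimate what its title names. Troughs begin on Day 11, after the stated plateau for balovaptan (about 7 days) and M3 (10 days), so the data can only confirm that a plateau holds.

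The consequence is minor: this is a secondary PK output, and balovaptan is expected to be within about 3% of plateau by Day 11.

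**What to change.** In SAP 16.2.2.1 and Table 14.2.2.3:

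1. Add a subject effect to the model (random or repeated) and amend the pseudo-code to match.
2. Set the Day 13 vs 14 divisor to 1.
3. Exponentiate each contrast to a geometric mean ratio (day over mean of later days) with a two-sided 90% CI.
4. Pre-state a tolerance. Conclude steady state from a given day only if that day's CI and those of all later contrasts lie within it. The range 0.80 to 1.25 is illustrative; the choice is the sponsor's.
5. State that a CI covering 1 does not by itself show steady state.
6. Report the result as confirmation that steady state holds over Days 11 to 14, not as an estimate of time to steady state, and retitle the table accordingly.

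Items 1, 2 and 4 belong together. Under the tolerance with the code left uncorrected, a 25% one-day rise would pass the Day 13 vs 14 contrast in 53% to 100% of simulated runs (between-subject SD 0.3 to 0.6, within-subject 0.10 to 0.25).

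The cost is a few lines of text and code before database lock, with no new data. The downside is that a tolerance must be fixed in advance and a noisy analyte may be reported as not shown.
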